## 7.0 CONDUCT OF THE STUDY

### 7.1 Ethics and Regulatory Considerations

This study must have the approval of a properly constituted Institutional Review Board (IRB) or Independent Ethics Committee (IEC), and the Institutional Biosafety Committee (IBC). Before the investigational drug is shipped to the investigator, the investigator will provide Gradalis, Inc. with a copy of the IRB or IEC and IBC approval letter stating that the study protocol and informed consent form have been reviewed and approved.

### 7.2 IRB and IBC

This trial can be undertaken only after review and full approval of the protocol and a Patient Informed Consent Form has been obtained from a properly constituted IRB. This written approval must be dated and it must clearly identify the protocol, any amendments, the Patient Informed Consent Form, and any applicable recruiting materials and subject compensation programs approved.

Since this trial will also be reviewed by a properly constituted IBC, this trial will not be undertaken until the protocol has been reviewed and received full approval from a properly constituted IBC. This written approval must be dated and it must clearly identify the protocol and any amendments.

The decision concerning the conduct of the study will be made in writing to the sponsor. Copies of this decision and of all IRB and IBC correspondence will be kept on file at the study site; copies will be provided to the Mary Crowley Research Office.

During the trial, the PI is required to send various documents to the IRB and IBC for review:

1. All protocol amendments and Patient Informed Consent Form revisions.
2. Reports of all Serious Adverse Events.

The PI provides Gradalis, Inc. with the necessary assurance that an IRB and IBC is responsible for the initial and continuing review and approval of the proposed clinical study in accordance with 21 CFR 312.60. At least once a year, the IRB and IBC will be asked to review and re-approve the clinical trial protocol; the request must be documented in writing. At the end of the trial, the PI will notify the IRB and IBC that the trial has been completed.

### **7.3 Written Informed Consent**

The informed consent document should meet the requirements of the latest version of the Declaration of Helsinki and any applicable regulations and guidelines. It must be approved by an IRB or IEC.

Prior to entry into the trial and before any protocol-required procedures are performed, the Investigator must explain the nature of the trial, its intended purpose, and the implications of participation to potential patients or to their legal representatives. They will be told about the possible risks and benefits, and the possible adverse experiences. They will be informed that patients' participation is voluntary, and that they may withdraw consent to participate at any time. They will also be informed that if patients choose not to participate in the trial alternative treatments are available; such refusal will not prejudice further treatment of their disease. Potential patients or their legal representatives must be given the opportunity to ask questions about the trial protocol and the procedures involved.

Finally, each patient will be told that his or her records may be accessed by authorized personnel of Mary Crowley, Gradalis, Inc. and other authorized individuals without violating the patient's confidentiality, to the extent permitted by the applicable laws and/or regulations. By signing the written Patient Informed Consent Form, the patient or his or her legal representative is authorizing such access. Following this explanation and prior to entry into the trial, the written,

dated, and signed Patient Informed Consent Form must be obtained from each patient or his or her legal representative; a copy will be given to the person signing the form.

#### **7.4 Confidentiality of Records**

The Investigator is required to retain, in a confidential manner, sufficient information on each patient (i.e., full name, current address, and social security number) so that the patient may be contacted by the FDA, Gradalis, Inc., or by Mary Crowley should the need arise.

#### **7.5 Modification of Protocol**

Any changes to this protocol that affect study objectives, study design, study procedures, patient population, or significant administrative procedures will require a formal amendment to the protocol. Any proposed protocol amendments must be sent in writing to the applicable IRB. Prior to implementation, an amendment must be approved by the Gradalis, Inc., and approved by the applicable IRB or IEC and IBC.

General administrative changes to the protocol are minor corrections and/or clarifications that do not affect the manner in which the study is to be conducted. Such administrative changes will be agreed upon by the Gradalis, Inc., and will be documented in a memorandum. The applicable IRB or IEC and IBC will be notified of administrative changes according to applicable IRB guidelines.

#### **7.6 Protocol Questions and Deviations**

When evaluating a potential patient or while a patient is on study, protocol questions can be sent to [[contact]](mailto:[contact]). Mary Crowley CRO will work with Gradalis in obtaining an answer / clarification. Please allow 24 hours for a response. For urgent questions affecting patient safety, please contact the Gradalis personnel by the phone provided in the Gradalis Contact Information section of the Study Reference Manual.

For Planned Protocol Deviation requests, the site will complete the Eligibility Inquiry/Planned Protocol Deviation Form and email or fax it to [[contact]](mailto:[contact]) or [contact]. If sent by fax, an email should be sent to the above email address to alert Mary Crowley of the fax. Mary Crowley CRO will work with Gradalis and the Medical Monitor to review the

request. Please allow 48 – 72 hours for review. Once complete, the form will be returned to the site.

## 8.0 EVALUATION OF TUMORS

### 8.1 Disease Evaluation

Disease recurrence will be evaluated in this study using the Response Evaluation Criteria in Solid Tumors Version 1.1 (RECIST) (unidimensional measurement) of the tumor lesions are used in the RECIST criteria (Eisenhauer, Therasse et al. 2009).

Disease recurrence is defined as the appearance of any measurable or evaluable lesion or as asymptomatic CA-125 levels greater than 35 U/mL at two consecutive measurements, at least one month apart. The time to recurrence is measured from date of first treatment until the first date that recurrence is objectively documented whether local, regional, or distant.

## 9.0 DRUG INFORMATION

### 9.1 Investigational Product

The Vigil™ vaccine is made up of irradiated autologous tumor cells which have been electroporated *ex vivo* with the Vigil™ plasmid designed to suppress expression of both the TGF $\beta$ 1 and TGF $\beta$ 2 proteins while simultaneously expressing rhGMCSF protein.

#### Vigil™ Vaccine Production

The Vigil™ Phase II ovarian vaccine cGMP manufacturing process is identical to prior Vigil™ vaccine cGMP manufacturing (BB-IND 14205) (Maples 2010). Surgically excised tumor is collected in the surgical field and placed in sterile saline and packaged for transport to the manufacturing facility. The tumor is mechanically and enzymatically dissociated into a single cell suspension. The cells are counted and then transfected with the FANG™ plasmid. The cells are incubated overnight to allow transcription of the FANG™ plasmid. The following morning the cells are harvested, washed, and then irradiated at 10,000cGy in a standard Blood Bank irradiator. The irradiated cell suspension is then enumerated, aliquoted and frozen ( $1 \times 10^7$  cells). The freeze media consists of

10% DMSO (dimethyl sulfoxide; Cryoserv USP; Bionichepharma US), 1% Human Serum Albumin (ABO Pharmaceuticals) in Plasma-Lyte A at pH 7.4 (Baxter). After freezing the cells are stored in the vapor phase of liquid nitrogen until all release testing is completed, all necessary approvals are obtained and the patient is ready for treatment.

## 9.2 Safety Analysis

The FANG™ plasmid employed in the generation of this autologous cell vaccine has been tested for identity, sterility, purity and strength.

### **Irradiated Gene Modified Tumor Cells**

To ensure safety, all gene-modified tumor cells to be used in patient vaccinations must be irradiated 10,000 cGy prior to freezing. This is the same irradiation process as for the TAG vaccine, BB-IND 13650 and prior vaccines (Belagenpumatumcel-L and GVAX® published trial results and BB-IND 13401 and BB-IND 12118) (Kumar 2009; Maples PB 2009; Maples PB 2009). The selection of this radiation dose is based on the desire to utilize the lowest possible radiation dose for the transfected cells to optimize the level and duration of bifunctional shRNAfurin transcription and GMCSF protein production and maximize the safety of vaccine cell injections at the same time. In addition, investigators have demonstrated that irradiating cultured tumor cells of different histologic origins at 10,000 cGy completely arrests tumor colony formation.

### **Preparation**

Reference the Study Reference Manual for vaccine preparation and handling information.

Drug concentrate: 1.0 x 10^7 cells per injection in a volume of 1mL.

Route of administration: Intradermal injection

### **Storage**

Frozen, unopened vials are stored in the vapor phase of Liquid Nitrogen.

### **Administration of vaccine**

Patients with viable cells in sufficient numbers for at least  $1.0 \times 10^7$  cells / injection for 4 doses will receive monthly intradermal injections of the tumor cell vaccine (as assigned cohort and available cell yield following tumor harvest and processing) as long as sufficient material is available. Patients who fail to achieve successful manufacturing of a minimum of 4 doses will not undergo treatment. The sites of injection will be rotated between the right and left upper arms. If the ipsilateral axillary lymph nodes were radiated or surgically resected during prior therapy, alternative sites (e.g., anterior thigh) will be used. The patient will be observed for at least 30 minutes (with a 10% window) following vaccination. During this observation period, vital signs will be taken every 10 minutes (with a 10% window). If clinically stable vaccine administration may continue for up to 12 doses given on a monthly basis as long as sufficient material is available.

### **9.3 Concomitant Therapy**

All concomitant treatments, including blood and blood products, must be reported on the source documentation. The following concomitant medications must be documented on the Con Meds page of the CRF:

- Prophylactic antibiotics
- Premedications
- Antifungals
- Antinauseants, antipyretics

Short term (<30 days) concurrent systemic steroids  $\leq 0.25$  mg/kg prednisone per day (maximum 7.5 mg/day) and bronchodilators (inhaled steroids) are permitted; other steroid regimens and/or immunosuppressives are excluded.

## **10.0 OCCUPATIONAL SAFETY**

Study medications are not expected to pose significant occupational safety risks to investigational staff under normal conditions of use and administration. However, precautions should be taken to avoid direct contact with study medication. Biosafety Level 2 practices shall be employed with this study medication. Reference the Study Reference Manual.

## 11.0 ADVERSE EVENTS

### 11.1 Adverse Event and Serious Adverse Event Definitions

#### Adverse Event

An AE is any untoward medical occurrence in a patient or clinical investigation subject administered a pharmaceutical product and that does not necessarily have a causal relationship with this treatment. An AE can therefore be any unfavorable and unintended sign (including an abnormal laboratory finding), symptom, or disease temporally associated with the use of a medicinal (investigational) product, whether or not related to the medicinal (investigational) product.

#### Serious Adverse Event

An AE (experience) or reaction occurring at any dose should be classified as a serious adverse event (SAE) if any of the following occur:

- Initial or prolonged hospitalization
- A life-threatening condition (i.e. an event in which the patient was at risk of death at the time of the event; it does not refer to an event which hypothetically might have caused death if it was more severe)
- Significant disability/incapacity (i.e. the AE resulted in a substantial disruption of the subject's ability to carry out normal life functions)
- Congenital anomaly/birth defect
- It does not meet any of the above serious criteria, but may jeopardize the subject or may require surgical or medical intervention to prevent one of the outcomes listed above.
- Death

#### Unexpected Adverse Event

An unexpected event is any AE that is not identified in nature, severity or frequency in the Clinical Investigator's brochure or the drug package insert.

## **Grading Adverse Events**

Adverse events (AEs) will be recorded throughout the trial. Toxicities and AEs will be graded and reported using the Common Toxicity Criteria for Adverse Events (CTCAE) Version 3.0 as linked in Appendix C. All AEs, regardless of severity, will be followed by the Treating Physician until resolution is satisfactory.

### **11.2 Attribution of Causality**

The relationship of each event to treatment will be assessed by the Treating Physician and recorded on the CRF.

### **11.3 Expected Side Effects**

Tumor cell vaccines have been previously administered to patients with cancer. Side effects were minimal, the most frequent of which included local reactions at the site of injection. Potential adverse events are listed below.

#### **Local skin reactions at the site of injection:**

Erythema, tenderness, induration, urticaria/rash, pruritus.

#### **Other expected adverse events:**

Fever, myalgias/arthalgias, chills/rigors, nausea, fatigue, headache, thrombocytopenia and other cytopenias, hyperglycemia, vomiting, hypotension, infection at the immunization site.

In addition there may also be a risk of autoimmune disease development, although to date no evidence of this has been seen in any vaccination study. There may also be worsening of tumor related symptoms secondary to immune mediated attack on patient's tumor.

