detectable autologous tumor specific cytotoxic CD8+ T-cell activity at baseline. Two patients showed ELISPOT reaction at baseline ( $\geq 10$  spots), but while one showed reactivity  $\geq 2$  times that of baseline at the Month 3 assessment, the other did not have a  $\geq 2$  times increase in ELISPOT spots, and thus was considered a negative responder. Twelve patients had an increase in immune response from a baseline mean of 6 IFN $\gamma$  producing T-cell spots to an end of Cycle 3 mean of 106 IFN $\gamma$  producing T-cell spots ( $p = 0.011$ ). The other 12 patient showed neither reactivity nor enhancement of immune response from a baseline mean of 3 spots through Cycle 3. These 2 populations were statistically different from each other at the end of Cycle 3 in ELISPOT response (106 spots vs. 3 spot,  $p=0.007$ ). Comparison of survival between the 12 patients demonstrating positive ELISPOT response and those 12 not demonstrating response at completion of Cycle 3 demonstrated a statistically significant increase in survival from time of procurement ( $p=0.040$ ) and time of treatment start ( $p=0.023$ , Figure 13a, b) in the former group. Additionally, patients who received  $\geq 3$  doses of Vigil™ and had a positive ELISPOT had better survival than patients who did not receive Vigil™ ( $p<0.001$ ).

[figure not shown]
**Figure 12.** IFN- $\gamma$  (ELISPOT) in FANG™ vaccine treated patients peripheral blood mononuclear cells in response to non-transfected autologous tumor cells. Blue lines indicate patients achieving  $\geq 10$  IFN- $\gamma$  producing lymphocytes (positive response) after 3 cycles of FANG™ vaccine. Red lines indicate patients not achieving positive ELISPOT response after 3 cycles of the FANG™ vaccine. (Data as of 01/08/13)

All patients demonstrating positive response after 3 complete cycles of Vigil™ vaccine who had long term assessment continued to show positive ELISPOT response during vaccine treatment and after discontinuation of vaccine therapy (Figure 12). Two patients who were in the non-responsive group at the end of Cycle 3 demonstrated a late positive response after 5 cycles of Vigil™ vaccine. One of these patients had advanced metastatic melanoma with survival of 490 days since treatment start, and the other had hepatocellular cancer with a survival of 738 days since treatment start.

a

b

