### **Off Treatment Assessments**

The following evaluations will be performed within 30 days following the last Vigil™ administration and within 30 days of disease recurrence (unless otherwise specified):

1. A physical examination, including vital signs and body weight.
2. Toxicity assessment (adverse events) (Vigil™ administered patients only).
3. Assessment of concomitant medications taken.
4. Assessment of PS on the ECOG scale (see Appendix A).
5. A tumor clinical assessment of the patient's disease (i.e., by physical examination).
6. Radiological assessment of disease status (i.e., chest X-ray, (chest CT or MRI only if indicated), pelvic/abdominal CT or MRI) used to stage the extent of disease. (within 45 days of the last injection or disease recurrence)
7. A CBC with differential and platelet count.
8. CA-125 tumor assessment.
9. Serum chemistry and electrolytes.
10. Serum for immune function analysis consisting of ELISPOT analysis of cytotoxic T cell function to autologous tumor antigens.

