### **Follow Up Assessments**

If the Vigil™ vaccine is discontinued (for reasons such as completion of all available doses of vaccine, intolerable toxicity, treatment interruption of more than 4 weeks, intercurrent illness, protocol deviation at PI's discretion), the patient will be contacted by phone every 3 months after the end of study visit for:

- disease status
- request of medical records, when applicable (laboratory findings, radiological scans, and progress report)
- documentation of 2nd line therapy
- recording of response and duration of response to that therapy
- survival
- assessment of any additional cancer treatments)

**Note:** Patients who die or withdraw consent are considered **off study** and no further information except survival data will be collected.

Based on findings during the study or during the follow up portion of the trial, Gradalis may request for additional blood and / or tissue samples from the research participant. Collection of whole blood (40ml) and / or tissue samples (via biopsy or clinically indicated surgical removal) will be **optional** and used to study the effects of the study agent (included, but not limited to testing of biomarkers, predictors or biological responses, toxicity, relationship between genotype and study agent responses).

Should Gradalis request for additional blood or tissue, the clinical site will present the option of the procurement to the participant and obtain written informed consent.

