## 11.4 Recording of an Adverse Event

Adverse events will be recorded for the duration of a patient's study treatment, and for up to 30 days following the last study treatment. All AEs, regardless of causal relationship are to be recorded in the CRF and source documentation. Additional information about each event, such as treatment required, eventual outcome, and whether or not therapy had to be interrupted or dosages reduced, will also be recorded on the CRF.

Pre-existing conditions will be recorded at baseline on the Medical History Form. If a pre-existing condition does not change, it does not have to be reported as an AE on subsequent cycles.

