## APPENDIX B

## Schedule Of Assessments

Procedure	Prestudy	Screening	Monthly (q 28±3 days)	End of TX	Follow-Up
Informed consent	X	X			
Phone Contact	X 				
Medical History	X	Interval Medical History within 4 weeks			
Physical Examination	X	X	X	X	
Toxicity (adverse events)			X	X	
Concomitant medications		X	X	X	
Performance Status	X	X	X	X	
Clinical Tumor Assessment		X	X	X	
Radiological Tumor Assessment (abdomen/pelvis) 	within 6 weeks	within 4 weeks		X	
CBC with differential	X	X	X	X	
HIV testing, if applicable		X			
CA-125 tumor assessment 	X	X	X	X	
Serum Chemistry	X 	X	X	X	
Immune Function Analysis	At tissue procurement and prior to the 1st and 3 rd cycles of chemotherapy post debulking	X	Months 2, 4, 6 prior to vaccine administration	X	
Urinalysis		X			
EKG		X			
Vaccine administration 			X		
Injection Site Assessment			Day 2 only		
FACT-O 		X	X		
Survival Status	X			X	X 

 Following tissue procurement, patients will be contacted every 6 weeks ±2 weeks to assess interest / eligibility of the main randomized portion of the trial and survival status.

 Radiographic assessments taken at baseline, ≤ 1 week prior to Cycle 4, at SOC intervals, and when CA-125 >35U/mL.

 CA-125 taken at baseline, monthly for the first year, every 3 months ± 2 weeks for the second and third year.

 Obtain from medical records from standard preoperative hematology and chemistry panels.

 The patient will be observed for at least 30 minutes (with a 10% window) following vaccination. During this observation period, vital signs will be taken every 10 minutes (with a 10% window).

 FACT-O assessment will be collected at baseline, Month 3, Month 6, Month 12, and Month 18.

 After EOT, subjects will be contacted by phone quarterly for disease status, medical records (when applicable), documentation of 2nd line therapy and recording of response and duration of response to that therapy, additional cancer treatments as well as survival.

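### After the 30-day window, non-serious autoimmune or vaccine-related events are not actively solicited, and the protocol's AE windows do not agree

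*Combined protocol and SAP*

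**What the plan says.** **The risk and the objective.** Section 11.3 (Other expected adverse events) states that "there may also be a risk of autoimmune disease development, although to date no evidence of this has been seen in any vaccination study". Section 5.4 makes autoimmune reactions a ground for stopping treatment. Section 3.2 lists enlargement of the safety database in patients with minimal disease as a secondary objective.

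**The recording window.** Section 11.1 (Grading Adverse Events) says "Adverse events (AEs) will be recorded throughout the trial". Section 11.4 says "Adverse events will be recorded for the duration of a patient's study treatment, and for up to 30 days following the last study treatment".

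**Follow-up.** Under Follow Up Assessments in Section 6.6, once vaccine is discontinued, "the patient will be contacted by phone every 3 months after the end of study visit for" a list of items: disease status, medical records when applicable, second-line therapy and the response to it, other cancer treatment, and survival. Appendix B footnote 7 gives the same content. Neither contains an AE item, and the toxicity row of Appendix B is marked for the monthly and end-of-treatment columns only.

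**Persistence of effect.** Section 1.10 reports that Phase I ELISPOT responders with long-term assessment "continued to show positive ELISPOT response during vaccine treatment and after discontinuation of vaccine therapy".

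**The concern.** The protocol names a risk that could appear late, and then stops asking about AEs soon after the last injection. Autoimmune disease can be non-serious at onset and need not appear during dosing. A patient who develops such a condition some months after the last dose would be telephoned every quarter, but the call as written would not ask about it.

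What is at stake is the safety objective. These patients are in clinical complete response and may live a long time after 4 to 12 doses. If few or no late autoimmune events are reported, the report cannot distinguish their absence from the absence of a question. The disagreement between Sections 11.1 and 11.4 adds to this, because sites may apply different windows and late events would then be collected unevenly.

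**Working it through.** The documents state no figure to reproduce. The check is a side-by-side reading, followed by simple arithmetic on timing.

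**Step 1. What is collected after dosing ends**

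| Place | What is collected | Limit |
|---|---|---|
| Section 11.1, Grading Adverse Events | AEs | Whole trial |
| Section 11.4 | All AEs | Up to 30 days after last treatment |
| Section 6.6, Off Treatment Assessments, item 2 | Toxicity assessment | Within 30 days of last dose, and within 30 days of recurrence |
| Section 6.6, Follow Up Assessments; Appendix B footnote 7 | No AE item | Quarterly calls |
| Appendix B, toxicity row | Toxicity | Monthly and end of treatment; nothing in Follow-Up |
| Section 11.5 | SAEs | Within 24 hours of awareness; the 30-day limit is stated for deaths, with no general end date |
| Section 12.1 | Serious or unexpected AEs associated with study medication | Any time after discontinuation |

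The recurrence assessment can fall after the Section 11.4 window has closed, and it has no column of its own in Appendix B. Sections 11.5 and 12.1 act on what the site already knows; neither has anyone ask the patient. What is left without active solicitation is the non-serious event that arises after the window and before recurrence, or at any later time in a patient who does not recur.

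**Step 2. When the Section 11.4 window closes**

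Inputs: 4 to 12 monthly doses (Section 6.4) and a window of at most 30 days, taken as 1 month. With the first dose at month 0:

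closure = (doses − 1) + 1 months

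- 4 doses: 3 + 1 = month 4
- 12 doses: 11 + 1 = month 12

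**Step 3. Gap to the recurrence assessment, for a patient recurring at the median**

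Inputs: assumed control medians of 16 months (Stage IV or suboptimal Stage III) and 24 months (optimal Stage III), from Section 13.1. I take these to run from first dose, as TTR does in Section 13.3.

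gap = median − closure

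| | Median 16 months | Median 24 months |
|---|---|---|
| 12 doses | 16 − 12 = 4 months | 24 − 12 = 12 months |
| 4 doses | 16 − 4 = 12 months | 24 − 4 = 20 months |

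**Step 4. Check with the 28-day cycle in Appendix B**

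- 4 doses: 3 × 28 + 30 = day 114
- 12 doses: 11 × 28 + 30 = day 338
- Medians at 30.4375 days per month: 16 months = day 487; 24 months = about day 730
- Shortest gap: 487 − 338 = 149 days
- Longest gap: 730 − 114 = 616 days

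This is about 5 to 20 months, so the answer hardly depends on how a month is counted.

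**Step 5. Patients who do not reach a recurrence visit**

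The documents give no distribution. If recurrence were exponential from first dose at the assumed medians, the share still recurrence-free at 36 months would be 2^(−36/16) = 0.21 to 2^(−36/24) = 0.35. For that minority the recurrence assessment supplies no late cover in the first three years.

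**The case against.** The strongest reply is that late cover exists and is broader than the calls suggest.

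- **Recurrence visit.** A toxicity assessment is scheduled within 30 days of recurrence. This stands. It ends the gap for patients who recur, but schedules nothing before then.
- **Serious events.** Section 11.5 sets no general end date, so a serious late autoimmune event known to the site is reportable. This also stands, and it confines the point mainly to non-serious events.
- **Unexpected events.** A reader might infer that Section 12.1 cannot reach autoimmunity because Section 11.3 lists it. The documents do not support that: Section 11.1 defines an unexpected event against the investigator's brochure or package insert. The brochure is not among the documents, so whether Section 12.1 would reach such an event is unknown. It would still have to be known to the site and associated with study medication.
- **The two windows.** Section 11.4 can be read as the operative detail of a general sentence in Section 11.1. That is reasonable, but nothing says so, and the trial continues into follow-up after the 30 days.
- **Other sources.** Records requested at follow-up, or the FACT-O item on treatment side effects (to month 18 or recurrence), might bring an event to light. Neither is AE collection.
- **Biology.** The ELISPOT finding is reactivity to autologous tumor cells. It makes a late effect plausible; it does not show autoimmunity. Section 1.10 reports no evidence of long-term toxicity in Phase I follow-up of more than three years.

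**Conclusion.** The point holds in a limited form. Non-serious autoimmune or vaccine-related events with onset after the Section 11.4 window and before recurrence, or at any later time in patients who do not recur, are not actively solicited and can go unrecorded. The gap is about 4 to 20 months for a patient recurring at the median, and longer for those who stay recurrence-free. This rests on monthly dosing without delay, 4 to 12 doses, and the protocol's assumed control medians counted from first dose. If the vaccine delays recurrence, the gap lengthens.

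Three stronger readings are not supported:

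- A reader might measure the gap against the three-year CA-125 schedule and conclude that most of it lacks solicited AE collection for every patient. Section 6.6 runs CA-125 only until recurrence, when a toxicity assessment is due, so that base fits only patients who remain recurrence-free.
- A reader might infer that this trial could not match the long-term safety follow-up cited from Phase I. The documents do not say how late AEs were collected there.
- A reader might infer that late autoimmunity is expected or has been seen. Nothing in the documents shows this.

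The primary endpoint and on-treatment safety monitoring are unaffected. This is an inexpensive improvement that bears directly on a stated secondary objective.

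**What to change.** 1. Add one scripted item to the existing quarterly call, in Follow Up Assessments (Section 6.6) and in Appendix B footnote 7: any new autoimmune or immune-mediated diagnosis, or any other event thought to be related to Vigil, with its onset date and any intervening cancer therapy. Record the answer on the CRF, including a negative answer, so that absence of events can be distinguished from absence of a question.
2. Reconcile the AE windows in Sections 6.6 (Off Treatment Assessments), 11.1, 11.4, 11.5 and 12.1 and Appendix B. One workable form is all AEs to the end of the 30-day window, then autoimmune and vaccine-related events for as long as the calls continue. State how toxicity found at the recurrence visit is recorded, and show that visit in Appendix B.

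The cost is one question on calls already planned and one CRF line, with no added visit or procedure. The downside is that some late events will be confounded by second-line therapy. That therapy is already recorded at follow-up, so it can be described alongside each event.
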